- Compare proportion of sample with perceived personal risk < base rate with proportion with perceived personal risk > base rate for treatment and control group. This does not suffer from the same sensitivity to outliers as the two measures proposed immediately above.
- Repeat the mean deviation test for an event with positive valence and similar average risk as 10year CVD risk. For this we use the probability of living past the age of 80 (section D). A positive mean deviation in this case would be consistent with pessimism bias. If we find this, then we cannot conclude that positive mean deviation in previous test is indicative of optimism bias.

- Test whether control group individuals state lower perceived personal risks (section D) than perceived base rates (section B) given not provided with base rate information.
- Compute share of unrealistically optimistic, accurate and unrealistically pessimistic individuals according to the definitions of Radcliffe and Klein (2002). Test whether there are significantly more unrealistically optimistic than unrealistically pessimistic individuals.
 - In particular, compute the ratio of predicted personal CVD risk to predicted CVD base rate (Globorisk), as well as the ratio of perceived personal CVD risk (section D) to perceived CVD base rate (section B). Individuals who provide a perceived risk ratio of more than 10% lower than their predicted risk ratio are defined as unrealistically optimistic. Likewise, individuals who consider themselves to be at higher relative risk than their predicted risk ratio (by more than 10%) are considered unrealistically pessimistic. Individuals whose perceived relative risk is within 10% of their predicted risk ratio are considered accurate.
 - Since a ratio is affected more by noise at small values than at large values, we will also define optimism / pessimism in terms of the difference between perceived personal and base rate CVD risk in comparison with the difference in the respective predicted risks.

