- Compute difference between perceived unconditional personal CVD risk and perceived conditional personal CVD risk for both control and treatment groups and regress on variables that indicate the respondents' smoking status, BMI and systolic blood pressure level. Test whether higher risk factor levels are associated with a higher difference between perceived unconditional and conditional CVD risks.

Q3: Do beliefs about susceptibility to CVD respond to information on predicted personal CVD risk?

[H3a] Beliefs about personal susceptibility to CVD are updated to incorporate information provided on objective CVD risk predicted from risk factor exposure.

Test:

- We test whether beliefs are updated consistently with Bayes rule such that,
 - posterior_i = $\lambda \cdot predicted_i + (1 \lambda) \cdot prior_i$ where $\lambda \in [0,1]$ is an updating weight representing the individual's willingness to abandon her own prior in favor of the provided risk information. To estimate λ for the 10-year personal CVD risk, we estimate:

$$(posterior_i - prior_i) = \lambda(predicted_i - prior_i) + \varepsilon_i, \qquad (3.1)$$

where the *prior* is perceived personal CVD risks of the information treatment group before being told their predicted risk obtained from Globorisk (D_T), posterior is the equivalent after being told the predicted risk (F_T) and the predicted is the Globorisk prediction of personal CVD risk. This yields an estimate of the extent of updating following the provision of only personal CVD risk information. $\hat{\lambda} = 1$ indicates complete revision of beliefs in which there is 100% reliance on the new information in the prediction and the prior to completely dismissed. $\hat{\lambda} = 0$ indicates no updating of beliefs. $\hat{\lambda} \in (0,1)$ indicates some updating, which can still be consistent with Bayes. For example, the respondent may weigh the new information and the prior in relation to the perceived sample size from which each is obtained.

• To test the response of risk perceptions to the different types of information provided, we estimate regressions of the general form: $p_i = \beta x_i + \gamma I_i + u_i$, where I_i is a dummy variable indicating whether a respondent has been allocated to the information treatment or to the control group and the interpretation of γ varies according to the definition of the dependent variable as follows:

Dependent variable (p)	Effect identified

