[H3d] Updating of beliefs is asymmetrical in response to positive information, i.e. $prior_i > predicted_i$, and negative information i.e. $prior_i < predicted_i$.

Test:

• We run the following regression:

$$\begin{array}{l} (posterior_{i} - prior_{i}) = \lambda_{1i}(predicted_{i} - prior_{i}) \times 1(predicted_{i} \leq prior_{i}) + \lambda_{2i}(predicted_{i} - prior_{i}) \times 1(predicted_{i} > prior_{i}) + \varepsilon_{i} \end{array}$$

and test $\lambda_{1i} = \lambda_{2i}$ against $\lambda_{1i} > \lambda_{2i}$. That is, under the alternative hypothesis, individuals who receive good news respond more than those who receive bad news. Such asymmetric updating is

consistent with the reinforcement of optimism bias. However, in light of Harris and Hahn (2011) and Shah et al. (2016), we cannot infer a mechanism for optimism bias from $\lambda_{1i} > \lambda_{2i}$ alone.

Q4: Do beliefs about susceptibility to CVD affect behavior in relation to lifestyles and the demand for preventive care?

[H4a] Beliefs play an important role in determining health behavior. Individuals are forward-looking and take into account their perceived susceptibility to CVD in deciding on their use of primary prevention and health lifestyles. Further, they use perceptions of the response of CVD risk to risk factors when deciding whether to change health habits such as smoking and diet/exercise.

Test:

- Run regressions of the form, y_i = βx_i + θp̂_i + ε_i, where the dependent variable is an indicator of a) whether the person has attended a health facility for a checkup, including blood pressure measurement and diagnostic tests, b) whether is taking medication for hypertension/diabetes, c) smoking (at all and intensity), d) BMI, e) exercise and possibly others. In one set of regressions, p̂_i will be the predicted value of the perceived personal CVD risk, which will be obtained from of one of the regressions described under [H3a]. That is, in the first stage, perceived personal CVD risk measured after the giving the treatment group information on the base rate and their predicted personal risk is regressed on the treatment group indicator. The IV estimate of θ tells us how behaviour responds to changes in CVD risk perceptions induced by information on those risks.

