To mitigate concerns that our respondents might be unfamiliar with the formal concept of probability, we will ask them to mark a number of coloured dots from 100 arranged in a square on a tablet screen (Figure 1). The respondent is asked a question, such as: "What do you think is the chance that you will have a heart attack or a stroke within the next 10 years?" The interviewer shows the respondent the square of dots and instructs her to mark the number that she thinks corresponds to that chance. When marked, the dots change colour. The respondent's reported probability, i.e. the number of marked dots, is also visible to the respondent as a number next to the figure. A similar approach has been used by Kerwin (2016), who uses a diagram of 100 pairs of stick figures representing couples, to elicit perceptions of the HIV transmission rate.

35

Figure 1 Belief elicitation tool

A potential concern when asking expectations questions is the tendency for probabilities to heap at the "focal" probability of 50%. This response may reflect the respondent's uncertainty about the probability rather than a precise evaluation that there is a 50:50 chance of the event occurring (Delavande and Kohler, 2009). In training questions, we follow the Health and Retirement Study and Kerwin (2016) by asking respondents who report 50% whether they really believe that the probability is 50%, or whether they are just not sure. This forces the respondent to consider what a response of 50% really means, and it gives us the option to control for respondents who have a tendency to give a focal response when they are not sure.

The risk perceptions module consists of eight sections. The first section familiarizes the respondent with probabilities and use of the belief elicitation tool. It starts with a simple explanation of probabilities using the example of the chance of a destructive earthquake within the following 12 months. The respondent then has to answer a number of expectations questions related to the example. The answers are used to test whether the elicited beliefs are consistent with basic properties of probabilities, such as monotonicity.

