Section 2 asks the respondent to report the chance that someone of the same age and gender will have a heart attack or a stroke within ten years. This is interpreted as the respondent's perception of the CVD base rate. Section 3, as well as Sections 5-7, is completed only by respondents in the information treatment group. These sections are described in the next section of this document. In section 4, the respondent is asked to report the chance that she will have a heart attack or a stroke in the next ten years. This is interpreted as the prior belief of personal CVD risk. In Section 8, the respondent is asked to report what her chance of a heart attack or stroke within ten years would be if she were to adopt healthier behaviour, i.e. to quit smoking (if a smoker) and to control blood pressure and weight.

After stating her perceived CVD risk in Sections 2 and 4 (and 6), the respondent is asked how confident she is in her answer on a five-point scale ranging from 1 (not at all confident) to 5 (extremely confident).

Respondents are likely to differ in how certain they are that the stated probability is close to the actual probability of having a heart attack or a stroke. Moreover, in Section 4 (and 6) the participant is asked how worried she is about having a heart attack or a stroke on a five-point scale ranging from 1 (not at all worried) to 5 (extremely worried).

5. Interventions

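### Reporting noise in the prior biases the updating weight from regression (3.1) upward, so a positive value is not by itself evidence of updating; the H3d split can show a spurious asymmetry of either sign

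*Combined protocol and SAP*

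**What the plan says.** Section 3.2, H3a, models the posterior as a weighted average of the predicted risk (weight λ) and the prior. It introduces the regression with "To estimate λ for the 10-year personal CVD risk, we estimate". Equation (3.1) is (posterior − prior) = λ(predicted − prior) + error, with no intercept. The prior is the information arm's first report of personal risk (D_T), the posterior is the second report (F_T), and predicted is the Globorisk figure.

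The plan says of this regression: "This yields an estimate of the extent of updating following the provision of only personal CVD risk information". An estimate of zero "indicates no updating of beliefs"; a value strictly between 0 and 1 is read as some updating.

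H3c repeats (3.1) with λ varying by education, predicted risk, confidence and worry. H3d splits the same regressor by its sign and tests λ1 = λ2 against λ1 > λ2: "under the alternative hypothesis, individuals who receive good news respond more than those who receive bad news".

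H3a has two further tests: an arm comparison of F_T with D_C, and a before-after comparison of F_T with D_T.

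Section 4 describes the answers. Respondents "mark a number of coloured dots from 100 arranged in a square on a tablet screen". It also states: "Section 3, as well as Sections 5-7, is completed only by respondents in the information treatment group". The second report of personal risk is section 6 of that module (F in Table 1), so controls give no posterior.

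**The concern.** D_T is a single answer about a probability, from a sample that section 4 describes as having limited schooling and numeracy. The plan accepts elsewhere that such answers are noisy. Under H2f it adds a second measure of optimism, with the reason: "Since a ratio is affected more by noise at small values than at large values". Equation (3.1) has no comparable protection.

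Suppose a respondent happens to report too high a prior. The change to the posterior is then too low, and so is the gap to the prediction. The two move together, and the regression reads that as updating. The reading of a zero estimate therefore fails in the direction that favours the hypothesis.

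The weight is also the quantity that H3c compares across groups and H3d compares between good and bad news. If noise differs by education or confidence, H3c can show differences in updating that are only differences in noise. H1b already hypothesises that violations of probability rules vary with education.

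**Working it through.** **No plan figure to reproduce for λ.** The documents give no value for λ, for reporting noise, or for power on beliefs. The nearest figure is the information-arm size of 287 (Table 6, mean CVD risk). From 1/n = (0.2/2.802)²/(1.9 × 0.64) − 1/1,306 = 0.003424, n = 292, within 2% of 287. I use 287 only as a sample size. It is a follow-up number; (3.1) uses baseline data, so somewhat more respondents would be available.

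**Algebra.** Let t be the true belief and d = predicted − t. Reported prior = t + e1 and reported posterior = t + Ld + e2. Both errors have variance s² and correlation r, and are independent of d. The outcome is then Ld + e2 − e1 and the regressor is d − e1. With k = s²/(E[d²] + s²), the no-intercept OLS estimate tends to

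L(1 − k) + k(1 − r).

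- No updating (L = 0): s²(1 − r)/(E[d²] + s²). This is positive unless s = 0 or r = 1.
- Independent noise (r = 0): L + k(1 − L), which is above L for every L below 1.
- Partly repeated noise: above L only when L < 1 − r.

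**Size under assumed inputs.** Reported beliefs have mean 25 and SD 18, predicted risk has mean 11.35 (the plan's figure) and SD 6, the two are independent, and r = 0. The denominator is (25 − 11.35)² + 6² + 18² = 186.3 + 36 + 324 = 546.3. The noise variance is (1 − reliability) × 324.

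| Reliability of prior | s² | λ estimate if nobody updates |
|---|---|---|
| 0.9 | 32.4 | 0.06 |
| 0.8 | 64.8 | 0.12 |
| 0.7 | 97.2 | 0.18 |
| 0.6 | 129.6 | 0.24 |

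With a true weight of 0.4 and reliability 0.8, the estimate is 0.4 × 0.881 + 0.119 = 0.47. With r = 0.5 the table entries halve; with r = 1 they are zero. With the plan's own SD of one fifth of the mean (2.27), the denominator is 515.5 and the range is 0.06 to 0.25.

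**How often zero is rejected.** Simulated with n = 287, no updating, true-gap SD 10, mean gap −10 to +10, noise SD 5 or 10, and r = 0 or 0.5, λ = 0 is rejected in 81% to 100% of runs. Clustering is ignored. Under the same model (noise SD 5, r = 0, mean gap +5), F_T v D_C rejects 5.0% of the time and the before-after comparison 5.2%.

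**H3c.** If nobody updates, a group with reliability 0.9 shows 0.06 and one with 0.6 shows 0.24, an apparent difference of 0.18.

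**H3d.** No updating, normal gap with SD 10, noise SD 5, r = 0. Gap = predicted − true belief.

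| Mean gap | λ1 (good news) | λ2 (bad news) | One-sided rejection for λ1 > λ2 |
|---|---|---|---|
| +10 | 0.39 | 0.10 | 81% |
| +5 | 0.28 | 0.14 | 55% |
| 0 | 0.20 | 0.20 | 4.7% |
| −5 | 0.14 | 0.28 | 0% |

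Skew matters too. On a 0–100 integer scale with skewed beliefs and noise SD 5, a mean belief of 6 gives 0.49 v 0.23, and a mean of 20 gives 0.06 v 0.39.

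**Check of the remedy.** Use (predicted − section B belief) as instrument for (predicted − prior), with an intercept. With no updating the IV estimate tends to [cov(eB, e1) − cov(eB, e2)] / cov(instrument, regressor), where eB is the noise in the section B answer. This is zero when B and D share no noise beyond what F repeats. At n = 299 and reliability 0.8, simulation gives −0.001 (SD 0.057) for a true weight of 0 and 0.399 (SD 0.047) for 0.4.

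If 30% of the noise variance is shared by B and D but not repeated at F, the numerator is 0.3 × 64.8 = 19.4. With a true B–D correlation of 0.7, the denominator is 36 + 0.7 × 259.2 + 19.4 = 236.9 and the estimate is 0.08, against 0.12 by OLS. With a correlation of 0.3, the denominator is 133.2 and the estimate is 0.15, worse than OLS.

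For H3d at reliability 0.8 and no updating, splitting on D_T gives 0.10 v 0.31. Splitting on the section B gap but keeping OLS gives 0.10 v 0.25. Splitting on the section B gap with IV in each half gives about 0 v 0, and 0.40 v 0.40 when the true weight is 0.4.

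**The case against.** The strongest reply is that H3a does not depend on (3.1). The F_T v D_C and before-after comparisons do not put the prior on both sides, and both held nominal error under the same noise. That stands. A reader might infer that noise alone would carry H3a; the plan's other two tests do not support that reading. What remains is that they measure average shifts. Upward and downward revisions can cancel in them, they give no weight, and they do not serve H3c or H3d.

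A reader might also infer that noise will produce the good-news asymmetry that H3d looks for. It need not. The artefact belongs to the split regression, vanishes when gaps are symmetric about zero, and favours λ1 > λ2 only when beliefs lie below predictions. When beliefs lie above, it hides a real good-news effect. The caveat the plan attaches to H3d concerns the mechanism of optimism bias, not reporting noise.

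The size rests on assumed noise and beliefs, and a non-updater asked again minutes later may repeat the same number. Both points stand. The IV is not assumption-free either: B and D use the same tool in the same module, so shared noise is plausible.

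Finally, the principal outcome, H5a and H6a do not use λ, and the first stage in H4a uses the treatment indicator. The point is confined to the beliefs mechanism.

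**Conclusion.** The concern holds in limited form. OLS on (3.1) does not centre on zero when nobody updates, unless the prior is free of noise or its noise is repeated exactly at F_T. The plan's readings of a zero estimate and of a value in (0,1) are therefore unsafe, and no control posterior exists to calibrate them. Under the stated assumptions (independent noise, reliability 0.9 to 0.6) the bias under no updating is about 0.06 to 0.24; the documents cannot fix it, and it may be zero. With independent noise, OLS is an upper bound for weights below 1; with partly repeated noise, only for weights below 1 − r.

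H3c can show spurious heterogeneity where noise varies with the characteristic. H3d can show a spurious asymmetry in either direction. The documents do not support a claim that H3a as a whole, or the trial's main results, are compromised.

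**What to change.** 1. In H3a, state that the OLS weight from (3.1) is biased upward by reporting noise when nobody updates, and drop the reading of a positive value as evidence of updating. Rest the H3a conclusion on F_T v D_C and the before-after comparison.
2. Beside OLS, report (3.1) and its H3c versions with an intercept and by IV, with (predicted − section B belief) as instrument for (predicted − prior).
3. For H3d, split on the sign of the section B gap and also apply the IV with an intercept within each half. Changing the split alone leaves most of the artefact. Say that news is then defined against the belief held before the base-rate information of section C.
4. State the IV assumption: B and D share no reporting noise beyond what is repeated at F.

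**Cost.** Analysis wording only, on data already planned. Intervals widen (simulated standard error about 0.06 for the overall weight at n = 299). The H3d halves will be uneven. Under the assumptions above, the section B gap has mean −13.65 and SD √(36 + 324) = 19.0, so about 24% of respondents (roughly 71 of 299) fall in the bad-news half, and that estimate will be imprecise. If the IV assumption fails, the IV can be as biased as OLS or more so, which is why both should be shown.

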D _T , D _C	Effect of base rate CVD risk information on perceived personal CVD risk.

F_T, D_C	Effect of information base rate + personal CVD risk information on
	perceived personal CVD risk.
H _T , H _C	Effect of base rate + personal + reduced risk factor CVD risk information
	on perceived personal CVD risk if reduced risk factors.
F_T - H_T , D_C - H_C	Effect of information on change in CVD risk if reduced risk factors on
	perception of that change.

- Using the treatment group only, we obtain an alternative estimate of the effect of being informed of predicted personal CVD risk on perceived personal CVD risk by regressing the latter on an indicator of whether it is measured prior to or after receiving personal risk information. That is, a simple before-after comparison: $p_i = x_i \beta + \gamma 1 (p_i = F_{Ti}) + u_i$, $p_i = D_{Ti}$ or F_{Ti} .
- We will run similar regressions to test for updating of confidence about reported risks and worry about CVD risk. See the last point under [H5a] on the relevance of the impact of information on belief confidence.

[H3b] Individuals who are exposed to the information intervention do not simply memorize numbers and percentages they are told in the treatment, but incorporate the information to update beliefs about event likelihoods related to CVD risks.

Test:

• Estimate the correlation between the prior-posterior change in perceived life expectancy and the prior-posterior change in perceived 10-year CVD risk. A negative correlation means that individuals update their life expectancy in a direction consistent with their revision to perceived personal CVD risk. For example, if the perception of CVD risk is raised, then life expectancy is reduced. We will repeat the same exercise for life expectancies conditional on experiencing a heart attack/stroke. As survival probabilities conditional on a CVD event are independent of CVD risk, a coefficient of zero is consistent with Bayesian updating. We use the same beliefs as described in [H3b] to test for updating following the provision of both base rate and personal CVD risks and the provision of only personal CVD risks.

[H3c] Updating of beliefs is heterogeneous with respect to education, predicted CVD risk, confidence about CVD risk estimates and worry about CVD events.

Test:

• Repeat regression (3.1) allowing λ to vary with the stated characteristics.

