5.2 Information on CVD risk

Information provided

Respondents randomly allocated to this treatment group will receive information on the predicted probability of having a heart attack or stroke within 10 years. The predictions will be obtained from the Globorisk tool (Ueda et al 2017). The reasons for using this algorithm are given in the next sub-section. All information will be provided within the risk perceptions module of the survey. Only this module will differ across the two treatment groups (information and lottery) and the control group. Information obtained from earlier modules will be retrieved automatically and used to make predictions of CVD risk consistent with the risk factor profile of the respondent in the information treatment group.

Three types of information on CVD risks will be provided to those in the respective treatment group: a CVD base rate, a personalized CVD risk and an optimal CVD risk. The CVD base rate will be predicted from the respondent's age and sex only. This information will be provided immediately after the respondents are asked to report the chance of someone of their age and gender having a heart attack or a stroke within ten years, and immediately before being asked to report the chance that they will have a heart attack or stroke within that period. The respondents will be presented with the information both as a chance of X in 100 and as the number of people (X) out of 100 the same age and sex as the respondent that doctors would expect to have a heart attack or stroke within ten years.

After reporting their own chance of having a heart attack or stroke within ten years, the respondents in the treatment group will be told the risk for someone with the same age, sex, smoking status, BMI and blood pressure as them. Each respondent will not be told that this is their own chance of having a heart attack or stroke. Rather, if the respondent is female, she will be told that out of 100 women her age, with the same

weight and blood pressure as her, and who (don't) smoke like her, doctors would expect X to have a heart attack or stroke within 10 years. Analogous information will be provided to male respondents. After being given this information, the respondent is asked again to report their 10-year CVD risk. This is interpreted as the posterior belief (after the provision of personalized information).

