- xvii) The proportion who have been advised by a doctor or other health worker be more physically active.
- xviii) The proportion of individuals overweight or obese (at baseline) who have been encouraged by a health professional to lose weight.

Since we do not have estimates of base rates for these outcomes that can be used to conduct power calculations, estimating effects on them will be contingent on ex-post analyses establishing that there is sufficient power. In addition, we will monitor whether those who attend a RHU/CHC receive advice

(/counselling) on smoking, alcohol consumption, diet and exercise, as well as being tested for hypertension, diabetes and hyperlipidemia, and whether they receive the respective medications.

Outcomes specific to information intervention

The information intervention will be used to estimate effects on beliefs about the risk of CVD. Specifically, we will estimate the effect of providing information on:

- xix) the CVD base rate on mean perceived 10-year risk of heart attack or stroke for someone of same age and sex;
- xx) the predicted CVD risk for someone with same risk profile as the respondent on mean perceived own 10-year risk of heart attack or stroke (posterior CVD risk);
- xxi) the predicted CVD risk for someone with the respondent's age and sex but the optimal risk profile on the mean perceived own 10-year risk of heart attack or stroke if were to adopt healthy lifestyle.

We do not have information necessary conduct power calculations for outcomes xix)-xxi) and so will carry out ex-post analysis to establish whether we have sufficient power to test for effects on these outcomes.

Outcomes not specific to CVD

If either of the intervention were to be successful in reducing exposure to CVD risk factors, then, in the long term, health gains will arise from it. Over a 6-7 month follow-up period, we do not anticipate that there will be sufficient time for general health affects to materialize and be apparent in a sample of the size studied. Nonetheless, we will measure general health using the SF-36v1. We will also measure labour outcomes (employment, hours and earnings), although we do not anticipate that the follow-up duration and sample size will be sufficient to detect any effects that may exist. Analyses of these outcomes will only be undertaken if an ex-post power calculation confirms that there is sufficient power, although this will not address the issue of the length of the follow-up.

8. Sampling

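### Outcome xxi credits the optimal-risk information alone with an effect that belongs to all three items of information, and the last H3a row is labelled too narrowly

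*Combined protocol and SAP*

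**What the plan says.** The letters are those of Table 1 in Section 3.2 (the risk perceptions module).

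- **What each arm receives.** Section 5.2: "Three types of information on CVD risks will be provided to those in the respective treatment group". These are the base rate (C), the risk for the respondent's own profile (E) and the optimal risk (G), given in that order. Section 4: "Section 3, as well as Sections 5-7, is completed only by respondents in the information treatment group". In that numbering, Sections 3, 5, 6 and 7 are C, E, F and G, so controls see none of the information.
- **When H is asked.** Table 1 places H last. It is asked once in each arm, and in the information arm only after C, E and G.
- **The regressor.** Under H3a it is a single "dummy variable indicating whether a respondent has been allocated to the information treatment or to the control group".
- **Third H3a row, H_T and H_C.** "Effect of base rate + personal + reduced risk factor CVD risk information", on the perceived risk if risk factors were reduced.
- **Last H3a row, F_T−H_T and D_C−H_C.** "Effect of information on change in CVD risk if reduced risk factors on" how that change is perceived.
- **Outcome xxi, Section 7 (outcomes specific to the information intervention).** The lead-in is "Specifically, we will estimate the effect of providing information on", and the item named is "the predicted CVD risk for someone with the respondent's age and sex but the optimal risk profile". The outcome is the respondent's perceived own risk under a healthy lifestyle.

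**The concern.** The third H3a row and outcome xxi describe the same comparison. One calls it the effect of three items of information, the other the effect of one. Only the first can be right, because the arms differ by all three items when H is asked.

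The last row has a related problem. Its label echoes Table 1's title for section G, whereas the two rows above it list their components with plus signs. F_T has already been moved by C and E, and H_T by C, E and G.

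H3a says these regressions are meant to show how perceptions respond to the different types of information. At stake is a conclusion about mechanism. A reader could credit or blame the optimal-risk message for a shift produced by the base rate and personal risk, or miss a real effect of that message because the earlier items offset it.

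**Working it through.** The plan gives no numerical figure for outcome xxi or the last H3a row, so there is none to reproduce. The check is a comparison of what has been received at each elicitation, then algebra, then an illustration.

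**Step 1. Information received before each belief is elicited** (Table 1; Sections 4 and 5.2)

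| Belief | Information arm | Control arm |
|---|---|---|
| D | C | none |
| F | C, E | not asked |
| H | C, E, G | none |

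Hence D_T v D_C reflects C, F_T v D_C reflects C+E, the within-arm change D_T to F_T reflects E, and H_T v H_C reflects C+E+G. No pair of elicitations of the same belief differs by G alone.

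**Step 2. Estimands.** Let a be the effect of C+E on perceived personal risk, b the effect of C+E on H, and g the effect of G on H.

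- Outcome xxi, H_T − H_C: b + g
- Last H3a row, (F_T − H_T) − (D_C − H_C): a − b − g

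If G does nothing (g = 0), these are b and a − b. The second is zero only if a = b.

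**Step 3. Illustration with g = 0.** From the documents: mean predicted risk 11.35 (Section 10.1). Assumed: prior D = 30 in both arms, weight λ = 0.6 on the prediction (C and E treated as one shift), and a perceived relative reduction r = 1/3 in both arms.

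- F_T = 30 + 0.6 × (11.35 − 30) = 18.81
- H_T = (2/3) × 18.81 = 12.54; H_C = (2/3) × 30 = 20
- H_T − H_C = −7.46
- Last row: (18.81 − 12.54) − (30 − 20) = 6.27 − 10 = −3.73

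**Step 4. Range with g = 0.** With proportional thinking, outcome xxi is (1 − r)λ(11.35 − D) and the last row is rλ(11.35 − D). For D from 5 to 40, λ from 0.25 to 1 and r from 0.2 to 0.5:

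- Outcome xxi: 0.8 × (11.35 − 40) = −22.9 to 0.8 × (11.35 − 5) = +5.1
- Last row: 0.5 × (11.35 − 40) = −14.3 to 0.5 × (11.35 − 5) = +3.2

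Both are negative when the prior exceeds 11.35 and positive when it is below.

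**Step 5. Would the trial detect it?** Simulation with 30 information and 136 control clusters of 10 (about the 299 and 1,361 of Table 6), intra-cluster correlation 0.1, assumed prior SD 20 and SD of r 0.1, answers truncated to 0–100, two-sided 5% test, g = 0:

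| D, λ, r | xxi rejects | Last row rejects |
|---|---|---|
| 30, 0.5, 1/3 | 100% | 100% |
| 30, 0.25, 1/3 | 94% | 91% |
| 20, 0.25, 0.2 | 52% | 42% |
| 8, 0.5, 1/3 | 14% | 12% |
| 30, 0, 1/3 (no item works) | 6.5% | 5.5% |

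In the D = 8 case, truncation at zero lifts the mean prior to about 12.6, close to the prediction, so the shift is small.

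**Step 6. The last row when G does work.** Let G raise r from 1/3 to 1/2 in the information arm, with D = 30.

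- λ = 0.6: H_T = 9.41, so the row is 9.41 − 10 = −0.6, almost nothing.
- λ = 0.5: F_T = 20.68 and H_T = 10.34, so the row is +0.3 (8% rejection in simulation).
- λ = 1: F_T = 11.35 and H_T = 5.68, so the row is −4.3 (100% rejection), opposite to G's contribution.

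**Step 7. Equal-point shifts.** If C+E lower both beliefs by 11.19 points (30 to 18.81, and 20 to 8.81), the last row is 10 − 10 = 0 and is sound for G. Outcome xxi is still −11.19.

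**The case against.** The strongest reply is that this is mostly a labelling matter, and several parts of it stand.

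- **The third H3a row is correctly labelled**, so the plan recognises the bundle in one place.
- **The last row's label admits another reading.** A change needs two numbers, so the label could mean E and G together. On that reading it omits only the base rate. It is still incomplete, but it does not plainly claim an effect of G alone as outcome xxi does.
- **Outcome xx.** A reader might infer that it has no valid estimator either. The documents do not support that. Equation 3.1 uses D_T to F_T and says it captures updating to personal-risk information only. H3a also adds a before-after regression, and it labels F_T v D_C correctly as base rate plus personal risk. What is missing is a statement that one of these is the estimator for xx.
- **A false fall in perceived benefit.** A reader might infer that the last row would report such a fall when none occurred. In the illustration the perceived absolute benefit really does fall, from 10 to 6.3 points, and the information causes it. The error would lie in crediting G.
- **The H4a model of rational behaviour.** It instruments the same difference with the arm indicator. A first stage uses the total shift and does not attribute it to G, so the mislabelling does not carry over. H5a likewise treats the intervention as a package.
- **Other tests of whether people see the benefit exist.** H2i compares the fraction with H below F_T (or D_C) between arms. In the illustration that fraction would be essentially unchanged.

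The contradiction between Section 7 and the H3a table remains, as does the absence of any contrast for G.

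**Conclusion.** The point holds as a mismatch between label and estimand. Outcome xxi, as worded, cannot be estimated: the design yields only the combined effect of C, E and G on H. The last H3a row reflects at least those three items and isolates G only if C and E together move F and H by equal points. Otherwise it can be non-zero when G does nothing, or near zero when G works.

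The structural conclusion rests on the documents alone. The sizes do not: about −7.5 and −3.7 points in the main illustration, and −22.9 to +5.1 and −14.3 to +3.2 over the range. They depend on assumed priors, updating weights and proportional thinking, for which the documents give no values, so neither size nor direction can be predicted.

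The principal outcome (predicted 10-year risk) and the H4a first stage are untouched. Outcomes xix to xxi have no planned power and are conditional on an ex-post check. What changes is what may be concluded about the optimal-risk message.

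**What to change.** Changes to the text, at no cost to data collection:

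1. Reword outcome xxi and the last H3a row as effects of the full information package (base rate, personal risk and optimal risk), so that Section 7 and the H3a table agree.
2. State that neither supports a conclusion about the optimal-risk information alone.
3. Name the D_T to F_T comparison already in H3a as the estimator for outcome xx.

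Only if the separate effect of G is wanted: ask the section H question in the information arm before G as well as after it, and analyse the change. This is one extra tablet question for about 330 respondents (299 from Table 6, divided by 0.9 for attrition). It must be in place before the baseline survey, where the information is delivered. The drawback is that asking twice may itself move or anchor the second answer.

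The proportional reduction, 1 − H/F against 1 − H/D, should not be used to isolate G. In the equal-shift case of Step 7, with G inert, it moves from 0.33 to 1 − 8.81/18.81 = 0.53, a spurious gain. H2f already warns that ratios are noisy at small values.
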